6.2 Assessment of safety

Any presentation at the emergency ward, home visit of emergency services, hospital admission and/or death is considered as a severe adverse event and will be documented as such. Furthermore, adverse events identified from the study data and/or from reporting by the patient will be documented. This is further specified in §7.

6.3 Focus group discussions

Qualitative data obtained from focussed group discussions will be analyzed using a two-step coding according to standards described elsewhere. (12, 13)

7 ADVERSE EVENTS

The pilot study will be performed while the remote rehabilitation program for COPD patients in Southwest Finland is enrolled as part of routine care for COPD patients. The aim of this study is to adjust the program to clinical experience. Strictly speaking, any adverse events related to the rehabilitation program are not related to the study, but to routine clinical care.

However, the pilot study will also be used to document adverse events related to the rehabilitation program, and these will be actively asked for as part of the rehabilitation program as well as part of the study. The participants can contact a healthcare provider via the application and are provided with a contact number for (suspected) adverse events during working hours and beyond. They are instructed to call the emergency services in case of any serious acute event.

Any presentation at the emergency ward, home visit of emergence services, hospital admission and/or death is considered as a severe adverse event (SAE) and will be documented as such.

Exacerbations of COPD can be expected in a significant proportion of patients due to the severe morbidity. Due to high prevalence of comorbidities, other SAEs may be linked to comorbidities. Any hospitalization for acute conditions that cannot be explained by COPD or the already present comorbidities, will be regarded as a suspected unexpected serious adverse reaction (SUSAR).

After 3 months and 6 months, and at any other point if clinically indicated, the investigators will carry out a safety check by analysing safety data of all included patients. In case of suspected safety issues, the head of the Department will be informed, as well as the Ethical Committee. It will then be considered whether continuation of the rehabilitation program is justified and sufficiently safe.

8 STATISTICS

8.1 Statistical hypotheses

8.2 Sample size

By recruiting 50 patients, we expect to recruit at least 12 patients from each of the following groups:

- According to exacerbations:
 - o Stable COPD patients
 - o COPD patients with acute exacerbations (AE-COPD)
- According to airflow limitation:
 - o GOLD 1-2 (Forced expiratory volume $\geq 50\%$ of predicted)

- GOLD 3-4 (Forced expiratory volume <50% of predicted)

8.3 Statistical plan and analysis

The majority of the study's data will take a descriptive approach. To determine statistical significance of the primary outcome the Mann Whitney U test will be applied for nonparametric data. Similarly, differences in continuous data between two groups will utilize the Mann Whitney U test, while the Kurskal Wallis test will be employed for comparisons involving more than two groups. Categorical data will be analyzed using either the chi squared test or Fisher exact test. There is a possibility of conducting multivariate analysis for non-parametric data to compute adjusted odds ratios if the data sets are deemed reliable due to their small size. A significance level of $p < 0.05$ will be considered statistically significant.

Data analysis will primarily leverage the most recent version of SPSS during analysis, but the investigator's preference may lead to the use of other established programs such as GraphPad and R. If faced with complex analysis, consulting a biostatistician might be considered, although this is not anticipated until after the study commences.

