3 STUDY DESIGN

3.1 Type and design of the study

This is a single-arm observational pilot study.

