3.2 General study outline and study schedule

Study subjects will be recruited from the 15th of April 2024 to the 30th of June 2026.

The rehabilitation program will be initiated preferably within one week but, at the latest within, 4 weeks from signing an informed consent, and the program will last up to 12 weeks. Follow-up will include 1 distant evaluation (questionnaires) at week 16 and a final visit at 26 weeks (+/- 2 weeks), including a 6-minute walking test. Follow-up may last up to 28 weeks from recruitment.

The final study report will be written in the years 2026-2027.

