4 SUBJECT SELECTION

4.1 Source population

The source population comprises patients enrolled in the remote rehabilitation program for COPD patients in Southwest Finland. Patients will be selected from the inpatient- and outpatient clinics of Tyks Department of Lung Diseases and Allergology for enrolment in the rehabilitation program.

Whether or not one participates in the pilot study will not influence one's ability to join the program. No control group will be recruited for this study.

Whether or not one participates in the pilot study will not influence one's ability to join the program. No control group will be recruited for this study.

Healthcare professionals working with this study population and guiding them using the mobile application will also be included in the study for interview and feedback on their experience with working with digital tools to interact with patients and guide them through the rehabilitation plan. This will be voluntary and will not affect in any way their position in the workplace.

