4.2 Number of subjects

Patients:

A maximum of 50 patients will be recruited for the pilot study.

Healthcare professionals:

All professionals involved in this study will be invited to participate in the feedback interviews.

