- b. The combination of patient input and clinical parameters is used to individualize the COPD therapeutics program for each patient. This will be done by the study investigators and healthcare professionals, and parts will be automatized. The automatically generated aspects will be evaluated and, if needed, adjusted by the study investigators and/or healthcare professionals.

- iii. **Phase 3: Individualized Program Development**
 - a. Patients who are identified as smokers are provided with a Cognitive Behavioural Therapy (CBT)-based program to support smoking cessation.
 - b. Based on the risk profile, participants are assigned to different types of breathing exercises, which are timed and progressively increased in intensity over time to improve lung function.
- iv. **Phase 4: Nutritional Advice**
 - a. Patients receive personalized nutritional advice based on **their input and nutritional status assessment**. The program aims to improve their dietary habits and overall nutritional status.
- v. **Phase 5: Physical Activity Program Initiation**
 - a. a physical activity program will start in the fifth week of the program. The intensity and duration of the program are determined based on their 6-minute walk test results according to the guidelines of the American College of Sports Medicine (ACSM) as applied in routine medical practice. Each patient receives an individually tailored program, which is approved by the TYKS physiotherapist. (11)
 - b. Over time, the program gradually increases the intensity and duration of the walking program to help patients build endurance.
- vi. **Phase 6: Strength Training**
 - a. After approximately eight weeks in the program, **depending on patients' clinical parameters** patients are introduced to strength training exercises to improve their overall physical strength and quality of life. Progression is slow and builds over time based on their risk profile.
- vii. **Phase 7: completing the program and follow-up**

- a. The training program finishes after 14 weeks. In this phase, the patient is interviewed about their experience
- b. In weeks 16 (+/- 2 weeks) and 26 (+/- 2 weeks), the symptoms will be scored with mMRC and St George respiratory questionnaire. In addition, a 6-minute walking test will be repeated in week 26 (+/- 2 weeks).

Tailoring of the program at the individual level

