6 OUTCOME VARIABLES

6.1 Assessment of efficacy

The single primary outcome measurement is distance in the 6 minutes walking test at 16 weeks in comparison to baseline to assess efficacy at the individual level. Secondary outcome includes 6 minutes walking test result at week 26 and St George Respiratory Questionnaire and 6 minutes walking test after 16 weeks and after 26 weeks in comparison to the result before initiation of the program. Other outcome measurements include the participant satisfaction, and other quantitative and qualitative measures of respiratory health and well-being.

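### The primary outcome is a within-patient change in a single arm, but section 8.3 tests it with the Mann-Whitney U test, which assumes two independent samples.

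*Protocol*

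**What the plan says.** Section 6.1 of the protocol defines the outcome: "The single primary outcome measurement is distance in the 6 minutes walking test at 16 weeks in comparison to baseline". It adds that the purpose is to judge efficacy within the individual. On design, section 3.1 says "This is a single-arm observational pilot study" and section 4.1 says "No control group will be recruited for this study". On size, section 4.2 says "A maximum of 50 patients will be recruited for the pilot study".

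Section 8.3 assigns the test: "To determine statistical significance of the primary outcome the Mann Whitney U test will be applied for nonparametric data". The next sentence deals with group comparisons: "Similarly, differences in continuous data between two groups will utilize the Mann Whitney U test". The other methods named are Kruskal-Wallis, chi-squared, Fisher's exact test and a possible multivariable analysis giving adjusted odds ratios. The significance level is 0.05; whether it is one- or two-sided is not stated.

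**The concern.** Every patient supplies both values in the primary comparison, so the baseline and follow-up distances are dependent. The Mann-Whitney U test takes its standard error from two unrelated samples. Applied here, it would treat up to 50 pairs as up to 100 different people and ignore the correlation within patients.

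At stake is the study's one formal efficacy claim. Section 2 lists improved exercise capacity among the objectives, the sample is capped at 50, and section 8.3 asks for a significance test of this outcome. An improvement that is real but modest could be reported as not significant only because the pairing was discarded. Section 8.3 also does not expect to consult a biostatistician until after the study has begun, so it plans no earlier step at which this would be noticed.

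**Working it through.** **Which comparison does the sentence govern?** Section 6.1 compares follow-up with baseline in the same patients, and sections 3.1 and 4.1 rule out a second sample. The sentence in 8.3 is about the primary outcome itself, because two-group differences get their own rule in the sentence after it. The named test therefore does not fit the defined comparison.

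**Is there a figure to reproduce?** No. The protocol gives no power, effect size, SD or correlation. Section 8.2 supports the number 50 only by expected subgroup counts of at least 12. The inputs below are assumptions, shown as a range:

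- n = 50 pairs (the cap in section 4.2), with 40 and 30 complete pairs as variants
- two-sided 0.05
- bivariate normal data with equal SDs, change expressed in between-patient SDs
- correlation ρ between baseline and follow-up, mainly 0.5 to 0.9

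**Analytic approximation (z-tests).** For a mean change in SD units:

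- Standard error assumed by an unpaired test: √(2/n) = √(2/50) = 0.200
- True standard error for paired data: √(2(1−ρ)/n) = 0.200 × √(1−ρ)
- Ratio of true to assumed: √(1−ρ) = 0.71 at ρ = 0.5, 0.55 at 0.7, 0.45 at 0.8

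The true error rate of the unpaired test is 2 × [1 − Φ(1.96/√(1−ρ))]:

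- ρ = 0: 5%
- ρ = 0.5: 1.96/0.707 = 2.77, giving 0.56%
- ρ = 0.7: 1.96/0.548 = 3.58, giving 0.03%

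The unpaired test needs an observed mean change of 1.96 × 0.200 = 0.392 SD to reach significance, whatever the correlation. A paired test needs 0.392 × √(1−ρ): 0.277 SD at ρ = 0.5 and 0.124 SD at ρ = 0.9. For a true change of 0.3 SD at ρ = 0.5:

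- unpaired power = Φ((0.3 − 0.392)/0.1414) = 0.26
- paired power = Φ(0.3/0.1414 − 1.96) = 0.56

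This also explains why, for true changes below 0.392 SD, the unpaired test's power falls as the correlation rises.

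**Simulation of the actual tests** (10,000 to 20,000 runs per cell).

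With no true change and 50 pairs, Mann-Whitney rejects 5% at ρ = 0, 2.2% at 0.3, 0.7% at 0.5, 0.1% at 0.7, and 0.01% or less at 0.8 to 0.9. The signed-rank test stays at about 5%.

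Power for a 0.3 SD change, 50 pairs:

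| ρ | Mann-Whitney | Wilcoxon signed-rank |
|---|---|---|
| 0.5 | 24% | 53% |
| 0.7 | 19% | 75% |
| 0.8 | 16% | 90% |
| 0.9 | 11% | above 99% |

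Power by number of complete pairs and size of change (first figure at ρ = 0.5, second at ρ = 0.9):

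| Pairs | Change (SD) | Mann-Whitney | Wilcoxon signed-rank |
|---|---|---|---|
| 50 | 0.4 | 48–52% | 77–100% |
| 50 | 0.5 | 74–90% | 92–100% |
| 50 | 0.6 | 90–99% | 98–100% |
| 40 | 0.3 | 18–6% | 44–98% |
| 40 | 0.4 | 37–32% | 67–100% |
| 40 | 0.6 | 80–95% | 95–100% |
| 30 | 0.4 | 25–15% | 54–100% |
| 30 | 0.6 | 64–77% | 87–100% |

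**The case against.** **The test may be meant for subgroups.** Section 8.2 sets up stable against exacerbating patients and milder against more severe airflow limitation. A Mann-Whitney test of individual changes between such groups would be valid. That reading does not survive: 6.1 defines the comparison as against baseline, and 8.3 covers two-group differences in a separate sentence.

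**A paired test may be given in a statistical analysis plan that is not shown.** It may. The absence of a paired test from the protocol is therefore not a fault in itself; it shows only that nothing in this document corrects the test. The fault is that the protocol does fix a test for the primary outcome, and it is the wrong one.

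**This is a mostly descriptive pilot with no power target, and the error is conservative.** This is fair as to consequences. No stated operating characteristic is broken, no false claim of benefit is made more likely, and the data remain usable with the right test. How much power is lost depends on a correlation and an effect that the protocol does not give; with a weak correlation or a large change it would be small. But 8.3 does call for a significance test of this outcome, and a pilot status does not make an independent-samples test suitable for paired data.

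**The week-16 schedule is a different matter.** Agreed. The test is wrong whichever week applies, and the schedule conflict adds nothing to the weight of this point.

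**Conclusion.** The point holds. Section 8.3 assigns an independent-samples test to a paired primary comparison. That conclusion follows from the text of sections 3.1, 4.1, 6.1 and 8.3 and needs no assumption.

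The size does rest on assumptions. If repeat distances are positively correlated, the true error rate is below the nominal 5% (2.2% at correlation 0.3, 0.7% at 0.5), and power is lost. The loss is severe for changes of about 0.3 to 0.4 SD and minor at 0.6 SD or more with 50 pairs: 8 points at correlation 0.5 (90% against 98%) and about 1 point at 0.9. It grows as complete pairs become fewer. The direction of harm is a missed improvement, not a false one. The wording should be corrected before the analysis because it governs the only primary outcome.

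**What to change.** Replace the sentence in 8.3 with one that names a single paired method in advance, for example:

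> Change from baseline in 6-minute walk distance at the primary time point will be tested with the two-sided Wilcoxon signed-rank test at the 0.05 level and reported with the median change and its 95% confidence interval.

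If a paired t-test with the mean change is preferred, name that instead; do not leave the choice to the look of the data. Keep Mann-Whitney and Kruskal-Wallis for comparisons between subgroups. The change from baseline in the St George questionnaire is paired too and is best handled in the same way.

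The cost is a change of wording. No extra data are needed, and the software named in 8.3 runs paired tests.

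A separate correction is needed so that the pairs exist. Section 6.1 sets the primary walk test at 16 weeks. Section 3.2 says "Follow-up will include 1 distant evaluation (questionnaires) at week 16", and section 5 (Phase 7) says "a 6-minute walking test will be repeated in week 26", with no walk test listed for week 16. These three sections must be reconciled, which may affect the visit schedule.

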8.4 Qualitative analyses

The study will also gather qualitative data through focus group discussions with patients of 8-10 participants per group will be included and will continue until data saturation is reached. Discussions with healthcare professionals will be based on availability and might be one-on-one depending on doctor's schedules. These discussions delve into subjective experiences, perceptions, and perspectives regarding the digital COPD rehabilitation program. Patient discussions will explore their engagement, challenges faced, and perceived benefits, shedding light on the program's usability and impact on daily life. Simultaneously, interviews with healthcare providers will capture insights into the program's integration into clinical practice, perceived patient response, and potential areas for program enhancement. These qualitative interviews will provide a nuanced understanding of participant experiences and healthcare provider perspectives, enriching the study's findings beyond quantitative measures.

The qualitative data will be analyzed using ATLAS.ti, a robust qualitative data analysis software. The software enables systematic coding and organization of textual and multimedia data, allowing for in-depth exploration and interpretation. Initially, the interview transcripts will be imported into ATLAS.ti and a systematic coding process will be employed to identify themes, patterns, and key concepts within the data. Through iterative coding and categorization, codes will be grouped to form themes and sub-themes, fostering a comprehensive understanding of participant perspectives and

experiences. The software's tools for qualitative analysis, such as network views and query functions, will be utilized to uncover relationships between codes and themes, facilitating the synthesis of rich, contextual insights from the qualitative data collected during the interviews.

8.5 Interim analysis

Interim analysis will be performed after 3 months and after 6 months. In case of safety concerns, continuation of the study will be critically appraised. For this purpose, external experts may be consulted.

9 QUALITY CONTROL AND QUALITY ASSURANCE

9.1 Information of study personnel and training

All investigators are familiar with the Helsinki Declaration and with the principles of Good Clinical Practice (GCP). All investigators are required to have successfully completed a GCP test within 2 years before the initiation of the study.

9.2 Monitoring and audits

The study will be subject to routine monitoring and audits as performed at the research department of Turku University Hospital, Department of Lung Diseases and Allergology

9.3 Protocol amendments

A protocol amendment will be made and submitted to the Ethical Committee in case of any significant change to the study protocol.

10 DATA HANDLING AND RECORD KEEPING

10.1 Source data

The study data will be obtained from Tyks patient records, from the COPD registry owned by the Wellbeing Services of County Southwest Finland and from the COPD rehabilitation program database (further addressed in §10.2), also owned by the Wellbeing Services of County Southwest Finland.

10.2 COPD rehabilitation database

Healthfox Oy provides the electronic service for the COPD rehabilitation database via the Microsoft Azure-service. The data in the COPD rehabilitation database is entered by patients using validated questionnaires, and relevant clinical data such as disease parameters are entered by healthcare

professionals. The data is stored on the Microsoft Azure-service in Ireland and Germany. The COPD rehabilitation database data protection is in line with the General Data Protection Regulation of the European Union. VARHA is the owner of the data. Healthfox Oy has the right to make quality improvement for the electronic service by using the patient data, if needed.

10.3 Pseudonymization of data and patient key

All study data will be pseudonymized and before storage and handling using a patient key. The patient key file will be stored in a locked space in the working room of the principal investigator. An electronic version of the patient key will be kept in the Microsoft Sharepoint of the Wellbeing Services of County Southwest Finland and will be only accessible to the medical doctors of TYKS involved in this study (HS, MK, RL, TF).

10.4 Electronic data collection

Pseudonymized clinical relevant data including sex, age, comorbidities, clinical characteristics of COPD, comorbidities will be collected via an electronic Case Report Form (eCRF) into an electronic database using REDCap via the University of Turku. Data collection rights are restricted to medical doctors of Tyks involved in this study (HS, MK, RL, TF), while right to correction is reserved to only HS and TF.

10.5 Data management

Pseudonymized study data will be exported from the REDCap study database to SPSS and/or R for statistical analysis. From there, selected data will be exported to graph design programs such as PRISM Graphpad. For this purpose, only the selected relevant data will be exported, to safeguard privacy of the study subjects. Data safety of REDCap is safeguarded by strict policy of the University of Turku.

10.6 Study subject registered

Only the patient identification code ('henkilötunnus') will be collected and stored in the patient key file, separate from the study data.

11 ETHICS

11.1 Ethical review

The study protocol will be reviewed by the Ethical Committee of the Wellness Services of County Southwest Finland for approval.

11.2 Ethical conduct of the study

As explained in §1, PR is an established and essential part of treatment for COPD patients, but availability and accessibility of PR is poor (locally in Turku & Southwest Finland, as well as in other parts of Finland). Virtual PR has been shown to be non-inferior to traditional PR, and may improve accessibility of PR. Therefore, virtual PR will be introduced in Southwest Finland in 2024. As highlighted in §2, this study is designed to facilitate a safe rollout of the remote rehabilitation program for COPD patients in Southwest Finland.

As the remote rehabilitation program for COPD patients in Southwest Finland will be part of routine medical care during this pilot study, participation will not pose patients at risk. The decision whether to participate in this pilot or not will not have any consequence regarding the possibility to participation in the rehabilitation program, nor any other treatments or therapy.

11.3 Subject information and informed consent

Patients will be shortly informed about the rehabilitation program and this pilot study by their treating physician. If interested, they will be further informed by one of the investigators of this study and they will receive the patient information letter. It is the responsibility of the recruiting investigator to check whether the patient has understood the methods and objectives of this study, before signing informed consent.

